The Effect of Theraworx/[pH]uel on night-time cramps and spasm symptoms including quality of life, depression and sleep quality

[figure not shown]
NCT03159260

Date of Document: 2/1/2018

Protocol

Potential subjects were recruited through various targeted methods including newspaper ads, fliers in pharmacies and physician offices, social media, sleep disorder support groups and word of mouth. Individuals were excluded from the study if they were pregnant, have been previously diagnosed with a Restless Leg Syndrome (RLS), previously diagnosed with schizophrenia or any other neurological disorder. Individuals were included in the study if they reported experiencing night-time leg cramps on average at least three times per week. Eligible individuals were scheduled to attend an initial assessment (Baseline) at a community-based physical therapy clinic. During this visit the study was described by a member of the research team and the individual was asked to provide written consent to participate in the protocol (RB#: SSR.2016.3). Following providing informed consent, the subjects were asked to complete a series of questionnaires about their demographic characteristics, symptoms associated with NLC including sleep quality, quality of life and depression. Once these questionnaires were completed all subjects engaged in a 14-day no treatment period in which they were told not to change their usual activities and treatments. Each morning during the 14 day no treatment period subjects were asked to complete a Symptom Log on which they documented the frequency and severity of night-time cramps they experienced the previous night.

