Subjects returned to clinic following this 14-day no treatment period (Post Control) and completed the same questionnaires excluding the demographic questions, since these demographic characteristics were not expected to change during the trial. Variables that were collected at the Post Control data collection point included the same measures of sleep quality, quality of life and depression as were collected at Baseline. Subjects were asked to refer their responses on these instruments to the previous 2 weeks following completion of the Baseline assessment. Once the subjects completed these instruments they were randomly assigned to one of two study groups by selecting 1 of 50 shuffled envelopes. Within 25 of these envelopes a card indicated "Foam A" and the remaining 25 envelopes contained a card indicating "Foam B." Subjects received two 3 ounce foam dispensers corresponding to their group assignment (Foam A or Foam B) and a 2-week Compliance and Symptom Log. The contents of these two foams remained blind to the subjects and the data collectors throughout the duration of the study until analysis. One of the foams contained Theraworx Relief™ (treatment) and the other contained a physiologically inert substance (placebo). Subjects were instructed to apply the foam they had been assigned to their entire upper and lower legs and feet using 8 pumps from the product dispenser per leg (upper thigh to foot) before retiring each evening for the next 14 days. If a subject experienced leg cramps after applying their assigned foam, they were instructed to reapply 2 pumps of the foam to the affected area in response to each event. Each morning during the 14 days in which subjects applied the foam they were asked to complete the Compliance and Symptom Log that documented the frequency and severity of night-time cramps and their use of the assigned foam they used to treat their night-time cramps the previous evening. Following 14 consecutive evenings of applying their assigned foam, subjects returned to the community clinic (Post Treatment), and return their completed Compliance and Symptom Log to the research staff. During this final visit subjects again completed the same measures of sleep quality, quality of life and depression that they completed during their Baseline and Post Control visits, referring their responses to the previous 2 weeks when they were applying the assigned foam to their legs. Subjects were compensated for completing the Baseline and Post Control and Post Treatment data collection visits.

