
Analysis:

Once all of the data were collected the contents of the foams were disclosed as Foam A containing the Placebo and Foam B containing the Treatment. The analysis was conducted in two phases. During phase 1 descriptive statistics were calculated to describe the demographic characteristics of the sample in order to assess the external validity of the results and the application of the findings to the larger population of patients suffering with NLC. Further descriptive analysis determined if the outcome variables met the assumptions of parametric statistics. The second phase of the analysis involved addressing the study hypotheses. Repeated measures analysis of variance (R-ANOVA) were calculated to determine if any of the outcome variables significantly ($p < .05$) differed between or within the two study groups over the duration of the study. Main or interaction effects detected by the R-ANOVA were explored further through calculating Tukey's post hoc comparisons. Finally, univariate comparisons (e.g. t-tests) determined if compliance rates or reported benefits differed between the study groups.

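### The repeated-measures tests on the three-visit outcomes have no sphericity correction, so the visit and group-by-visit F-tests can exceed 5%, modestly and by an amount the documents do not fix

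*Combined protocol and SAP*

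**What the plan says.** The Analysis section plans one method for all outcomes: "Repeated measures analysis of variance (R-ANOVA) were calculated to determine if any of the outcome variables significantly". The rest of that sentence sets the threshold at p < .05 and applies it to comparisons of the groups and to changes across visits alike. Main or interaction effects are then followed by Tukey comparisons. No sphericity test, epsilon adjustment, multivariate test or mixed model is named. The one safeguard is in the first analysis phase: "Further descriptive analysis determined if the outcome variables met the assumptions of parametric statistics". The assumptions are not listed, and nothing is said about what follows if one fails.

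The Protocol section fixes the visit structure. At the last visit "subjects again completed the same measures of sleep quality, quality of life and depression that they completed during their Baseline and Post Control visits", which gives three measurements per questionnaire. Allocation comes after the second of them: "Once the subjects completed these instruments they were randomly assigned to one of two study groups by selecting 1 of 50 shuffled envelopes". The envelopes are split 25 and 25.

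Cramp frequency and severity are collected differently, in nightly logs over two periods: "Each morning during the 14 day no treatment period subjects were asked to complete a Symptom Log", and then "Each morning during the 14 days in which subjects applied the foam they were asked to complete the Compliance and Symptom Log". How the logs are summarised for analysis is not stated.

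**The concern.** With three or more repeated measurements, the F-tests for visit and group-by-visit keep their nominal level only if all pairwise visit differences have the same variance (sphericity). Here one difference lies between two pre-randomisation visits, and two span the foam period. Variable response to applying any foam, placebo included, would make those two more variable even with no true treatment effect. Equal variances are possible, but nothing in the design favours them. If they are unequal, the uncorrected tests reject too often.

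This matters because randomisation follows the second visit, so a treatment effect on a questionnaire shows mainly as a group-by-visit interaction. The between-group main effect averages two untreated visits with one treated visit and dilutes it. A significant interaction also opens the way to the post hoc comparisons.

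**Working it through.** **Inputs.** From the documents: three visits, two groups, at most 25 per group, threshold .05. Assumed, because the documents give none: visit correlations and SDs, normal data, no dropout, and equal covariance in both arms.

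**Reference test.** The error degrees of freedom are (50 − 2) × 2 = 96, so the critical value is F.95(2, 96) = 3.091.

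**Epsilon.** Let a be the Baseline–Post Control correlation, b the correlation of each with Post Treatment, and s the Post Treatment SD relative to the earlier visits. The two orthonormal within-subject contrasts are uncorrelated, with variances

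λ1 = 1 − a and λ2 = (1 + a + 2s² − 4bs)/3,

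and epsilon = (λ1 + λ2)² / [2(λ1² + λ2²)].

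- a = 0.8, b = 0.5, s = 1: λ1 = 0.2, λ2 = 0.6; epsilon = 0.64/0.80 = 0.80.
- a = 0.8, b = 0.4, s = 1.3: λ1 = 0.2, λ2 = 1.033; epsilon = 1.521/2.216 = 0.69.

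**Size by the Box approximation**, P(F[2ε, 96ε] > 3.091): 0.050 at ε = 1; 0.056 at 0.9; 0.062 at 0.8; 0.069 at 0.7; 0.077 at 0.6; 0.085 at 0.5, the lower bound for three levels.

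**Size by simulation, group-by-visit test.** These are null trials, 200,000 per pattern (30,000 for the 0.9 / 0.4 row).

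| a / b / s | epsilon | uncorrected | Greenhouse-Geisser |
|---|---|---|---|
| 0.6 / 0.6 / 1 | 1.00 | 0.050 | 0.047 |
| 0.7 / 0.5 / 1 | 0.91 | 0.053 | 0.048 |
| 0.8 / 0.5 / 1 | 0.80 | 0.060 | 0.049 |
| 0.8 / 0.4 / 1.3 | 0.69 | 0.069 | 0.050 |
| 0.9 / 0.4 / 1.3 | 0.59 | 0.076 | 0.050 |
| near the bound | 0.50 | 0.085 | 0.049 |

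First-order autoregressive patterns give 0.052 (correlation 0.5, epsilon 0.93) and 0.056 (0.7, epsilon 0.88). The visit test behaves like the interaction test.

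**What is not exposed.** The between-group F had size 0.049 to 0.051 in all patterns. An outcome with two period summaries has one within-subject contrast, so epsilon is 1; its simulated size was 0.049 to 0.050. If the 28 nightly values were instead used as 28 levels, which is not stated, the Box approximation gives 0.063 under autoregressive correlation 0.3 and 0.090 under 0.5.

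**Post hoc comparisons.** The pooled error treats every visit difference as having variance λ1 + λ2. In the 0.80 pattern that is 0.8. The Post Control–to–Post Treatment change has variance 1 + s² − 2bs = 1.0, so its variance is understated by a factor of 1.0/0.8 = 1.25. In the 0.69 pattern the figures are 1.233 and 1.65, a factor of 1.34. One group comparison of that change against pooled error, at nominal 0.05 and before any Tukey adjustment, had simulated size 0.080 and about 0.09. A Greenhouse-Geisser p-value on the omnibus test does not repair this.

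**Power.** With an assumed Post Treatment difference of 0.5 of the Baseline SD (40,000 trials per pattern), power was as follows for the uncorrected test, Greenhouse-Geisser, and a Post Treatment contrast adjusted for Post Control:

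- epsilon 1.00: 0.51, 0.50, 0.57
- epsilon 0.80: 0.47, 0.44, 0.51
- epsilon 0.69: 0.34, 0.28, 0.30
- epsilon 0.59: 0.35, 0.28, 0.30

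The correction costs about 1 to 7 points. Part of that is power the uncorrected test gains only by exceeding its level. The adjusted contrast held its size (0.048 to 0.051) and beat Greenhouse-Geisser in every pattern.

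**The case against.** The documents give no covariance, so inflation cannot be shown, only bounded. Mild patterns leave the test almost at its level: 0.052 to 0.056 for epsilon 0.93 to 0.88. The argument that the two early visits correlate most is also open to doubt. Subjects kept their usual treatments in the control period, and Post Control and Post Treatment share a two-week recall frame that is not stated for Baseline. The Analysis section is a one-paragraph summary. Its assumption check could include sphericity, and the label R-ANOVA does not exclude an adjusted p-value. Finally, a shift of one or two points is small in a plan that tests several outcomes at .05 without naming a primary one.

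Most of this stands and sets the size of the point. It does not remove it. A higher Post Control–Post Treatment correlation would be a different departure from sphericity, not a return to it. A check with no stated consequence does not say which p-value is used.

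A reader might infer that the trial's F-tests do exceed 5%, or that every outcome is affected. The documents support neither. The first needs epsilon below 1 and no correction applied, and neither can be read from the text. The second fails for the between-group effect and for cramp outcomes summarised by period.

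**Conclusion.** The point holds in a conditional and limited form, and it is minor. For sleep quality, quality of life and depression, the plan does not say how the visit and group-by-visit tests are protected against non-sphericity, and the visit structure makes non-sphericity plausible. If no correction was applied, the true size lies between 0.05 and about 0.075 over the assumed patterns (epsilon 1.0 to 0.59) and cannot much exceed 0.085 for three visits. Post hoc comparisons that use the pooled error can be further off than the omnibus test. These figures assume normal data, the full 25 per arm, no dropout and equal covariance across arms.

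**What to change.** For each three-visit outcome, test the treatment effect with a single Post Treatment group contrast adjusted for the Post Control value. This can be an ANCOVA, or the same contrast from a mixed model with unstructured covariance. Neither needs sphericity.

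If the omnibus R-ANOVA is kept, state that the Greenhouse-Geisser p-value is the one used, and base each post hoc comparison on the error of that comparison, not on the pooled term. Also state how the nightly logs are summarised, since that decides whether the issue reaches the cramp outcomes.

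The cost is a sentence or two. The section describes the analysis in the past tense, but these results can be computed from data already collected. Under the assumed patterns, Greenhouse-Geisser takes about 1 to 7 points of nominal power from the omnibus test, and the adjusted contrast recovers some or all of that. The contrast does not test change within groups, which would need to be reported separately.

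### The Foam B versus Foam A contrast is not named as the efficacy test; time, group and interaction effects all count equally towards the hypotheses

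*Combined protocol and SAP*

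**What the plan says.** The Analysis section of the combined protocol and SAP states: "The second phase of the analysis involved addressing the study hypotheses". The method is a repeated measures ANOVA at p < .05, used to see whether any outcome "differed between or within the two study groups over the duration of the study". It continues: "Main or interaction effects detected by the R-ANOVA were explored further through calculating" Tukey comparisons. The hypotheses are not written out, and the effects are neither ranked nor tied to an efficacy conclusion. The only analyses described purely as between-group are the closing univariate tests of compliance and reported benefits, which are not given primary status.

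Three features of the Protocol section bear on this:

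- After the Baseline questionnaires, "all subjects engaged in a 14-day no treatment period"; foam use comes afterwards for everyone.
- Allocation happens at Post Control: "Once the subjects completed these instruments they were randomly assigned to one of two study groups". The Baseline and Post Control questionnaires therefore both precede treatment.
- Cramps are logged in both fortnights. For the first: "Each morning during the 14 day no treatment period subjects were asked to complete a Symptom Log".

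**The concern.** The title asks whether the product affects cramps, sleep, quality of life and depression. The blinded, randomised comparison with placebo foam is what can answer that, but the plan lets three different effects bear on the hypotheses.

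- **Time main effect.** Every subject goes through the untreated period first and foam second. A change common to both arms may reflect expectation on self-reported outcomes, a time trend or regression to the mean. The last is plausible because entry depends on symptom frequency: "Individuals were included in the study if they reported experiencing night-time leg cramps on average at least three times per week". It should, however, partly play out before the first cramp log.
- **Group main effect.** This compares arm means over all time points. Two of the three questionnaire visits and one of the two log periods come before any foam is applied, so a real effect is diluted.
- **Group-by-time interaction.** This does isolate the randomised contrast, but it has no priority over the other two.

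Two misreadings are left open. A significant time effect can be presented as a result on the hypotheses when the foams do not differ, and a non-significant group main effect can be taken as no benefit when there is one.

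**Working it through.** The plan gives no power calculation, SD, correlation or expected effect, so there is no figure of its own to reproduce.

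**Inputs from the documents:** 25 envelopes per foam (50 in all); threshold .05; three questionnaire visits; two log periods; allocation after the second questionnaire visit and the first log period.

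**Assumptions, not in the documents:** all 25 per arm analysed; a continuous normal outcome with SD 1; equal correlation ρ between visits or periods, 0.4 to 0.6; a shift s common to both arms in the foam period; a foam effect d (in SD) in the foam period only. Paired results below are for ρ = 0.4 / 0.6.

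**Step 1: dilution of the group main effect.** Averaged over questionnaire visits, the arm difference is (0 + 0 + d)/3 = d/3. Over log periods it is (0 + d)/2 = d/2. This depends only on the timing of allocation.

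**Step 2: identical foams with a shared shift.** Chance that the time effect has p < .05:

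- Questionnaires: noncentral F(2, 96), λ = 50 × (2/3) × s²/(1−ρ). At s = 0.3, λ = 5.0 / 7.5.
- Logs: noncentral F(1, 48), λ = 50 × s²/[2(1−ρ)]. At s = 0.3, λ = 3.75 / 5.625.

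| Shared shift s (SD) | Time effect, questionnaires | Time effect, logs | Interaction |
|---|---|---|---|
| 0 | 5% | 5% | about 5% |
| 0.1 | 9–12% | 10–12% | about 5% |
| 0.2 | 24–34% | 24–34% | about 5% |
| 0.3 | 49–67% | 48–64% | about 5% |
| 0.5 | 92–99% | 89–97% | about 5% |

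Simulated mixed ANOVAs (20,000 per cell) put the interaction rejection rate at 0.048–0.053 in every null cell. A separate simulation with ρ of 0.5 to 0.7 showed the same pattern: for questionnaires at s = 0.3, the time effect was significant in 57–81% of trials and the interaction in about 5%.

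**Step 3: power when Foam B has a real effect d.**

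- Group main effect, t(48). Questionnaires: mean difference d/3, variance of a subject's mean (1+2ρ)/3. Logs: d/2 and (1+ρ)/2.
- Interaction. Questionnaires: F(2, 96), λ = 25d²/[3(1−ρ)] = 8.89 / 13.33 at d = 0.8. Logs: F(1, 48), λ = 25d²/[4(1−ρ)] = 6.67 / 10.0.
- Adjusted post-treatment comparison (ANCOVA), simulated with 4,000 runs. The residual variance is 1 − 2ρ²/(1+ρ) = 0.771 / 0.550 with two pre-treatment visits, and 1 − ρ² = 0.84 / 0.64 with one log period. A closed-form approximation gives 88–96% and 86–93% at d = 0.8, close to the simulated values below.

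| Outcome, true effect | Group main effect | Interaction | Adjusted post-treatment |
|---|---|---|---|
| Questionnaires, 0.8 SD | 19–22% | 75–91% | 86–96% |
| Logs, 0.8 SD | 34–38% | 72–87% | 85–93% |
| Questionnaires, 0.5 SD | 10–12% | 36–51% | 49–62% |

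**The case against.** The strongest reply is that the right test is already planned. A two-group repeated measures ANOVA contains the group-by-time interaction, and its Tukey follow-up can include Foam B against Foam A at Post Treatment. The between-or-within wording may simply describe the two kinds of factor in a mixed ANOVA, and nowhere does the plan say that a time effect supports efficacy. The placebo arm and the blinding show comparative intent. On this view only the ranking is missing.

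Much of that is true, and it limits the point: the interaction is planned, and equal footing is an inference from effects that share one threshold and are joined without ranking. But the plan says these tests address the hypotheses, and main effects alone trigger follow-up comparisons. After a time effect, those would compare visits, not foams.

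Four further objections deserve an answer:

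- *The step 2 percentages are not this trial's error rate.* Correct. They are the power to detect a shift that really occurred. The time test is valid for time; the error lies in crediting the shift to the product.
- *The untreated fortnight reduces regression to the mean.* It does in part. Expectation that starts with the foam, and time trends, remain.
- *Adjustment rather than the interaction is a matter of efficiency.* Agreed. Both isolate the randomised contrast, and the interaction is an acceptable minimum.
- *The Analysis section is in the past tense, with the foams already disclosed.* If that reflects the actual timing, any contrast named now must be labelled as chosen after unblinding.

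**Conclusion.** The concern holds and should be fixed. The plan tests the randomised contrast but does not make it the basis for the efficacy conclusion, and it gives equal standing to one effect that cannot separate the foams and another that largely misses a real difference. The dilution to one third or one half follows from the design alone. The rejection rates and powers are conditional on 25 analysed per arm, the assumed correlations of 0.4 to 0.6, and the assumed shifts and effects. The pattern does not depend on the exact values: in every null case examined the interaction stays near 5% while the time effect's rejection rate climbs with the shared shift, and in every case with a true effect the group main effect has the least power of the three comparisons in step 3.

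**What to change.** State that the efficacy conclusion for each outcome rests only on the Foam B minus Foam A difference in the post-treatment period, adjusted for pre-treatment values: Baseline and Post Control scores for the questionnaires, and the no-treatment log for cramps. If the ANOVA is kept, name the group-by-time interaction as the efficacy test.

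In the same edit, take within-group differences out of the hypothesis test. The two changes must go together: deleting the within-group wording alone would leave a sentence that could be read as the group main effect, the weakest of the three comparisons. Report within-group changes descriptively, with confidence intervals and no efficacy claim.

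The cost is one or two sentences and one regression model per outcome; all the data are already collected. If the foams had been disclosed before the change, the report must say so. The real concession is that significant within-group improvement can no longer be presented as a finding on efficacy.

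### The R-ANOVA treats pre-randomisation scores as outcomes and names no Post Treatment contrast; one planned contrast adjusted for those scores is more precise and costs 1–2 degrees of freedom

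*Combined protocol and SAP*

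**What the plan says.** The Protocol section has sleep quality, quality of life and depression measured at Baseline, Post Control and Post Treatment. The Post Control set comprises the "same measures of sleep quality, quality of life and depression as were collected at Baseline". Allocation comes next: "Once the subjects completed these instruments they were randomly assigned to one of two study groups by selecting 1 of 50 shuffled envelopes". Of the 50 envelopes, 25 hold each foam.

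Cramp frequency and severity are logged in two 14-day periods, one on each side of randomisation: "Each morning during the 14 day no treatment period subjects were asked to complete a Symptom Log", and later "Each morning during the 14 days in which subjects applied the foam they were asked to complete the Compliance and Symptom Log".

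Phase 2 of the Analysis section uses repeated measures ANOVA, at the 5% level, to ask whether any outcome "differed between or within the two study groups over the duration of the study". Tukey's method is the only follow-up it gives: "Main or interaction effects detected by the R-ANOVA were explored further through calculating" such comparisons. It names no covariate, does not list the visits that enter the model, and picks out no between-group comparison at Post Treatment. The closing t-tests cover only compliance and reported benefits.

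**The concern.** Baseline and Post Control scores cannot carry a treatment effect, because nobody has been allocated when they are taken. They can serve as covariates, but the natural reading of the plan makes them levels of the outcome. Three things follow.

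- The group main effect averages two visits with no effect and one with the full effect, so it estimates a third of what is wanted.
- The group-by-time interaction is a proper randomised test. On three visits it has 2 df, one of which compares the groups on the change from Baseline to Post Control. It does not isolate the Post Treatment difference.
- That difference is left to Tukey comparisons whose family and error term are not stated, and the choice can change the result.

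For the cramp logs there is one period before randomisation and one after. On period summaries the interaction is then a test of change scores, which is less precise than adjusting for the no-treatment-period value. With at most 50 subjects, the trial has little precision to spare.

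**Working it through.** The plan gives no power calculation, so there is no figure of its own to reproduce.

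**Inputs from the documents.** 25 per arm (the envelope count) and a 5% level, taken as two-sided. Visits and timing of randomisation are as in the Protocol section.

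**Assumptions.** SD 1, equal correlation ρ between visits or periods, effect d (in SD units) only after randomisation, no dropout, and cramp logs reduced to one roughly normal summary per period. The documents give neither d nor ρ, so ranges are shown.

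**Questionnaires, three visits**

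- Group main effect: signal d/3, squared SE (2/25)(1+2ρ)/3, F(1,48).
- Interaction: F(2,96) with noncentrality 25d²/[3(1−ρ)]. At d = 0.6, ρ = 0.4 this is 25×0.36/(3×0.6) = 5.0, giving 49% power.
- Unadjusted 1-df contrast (Post Treatment minus the mean of the two earlier scores): variance 1.5(1−ρ), F(1,48). At ρ = 0.4 the SE is √[(2/25)×1.5×0.6] = 0.268, giving 59%.
- ANCOVA on both earlier scores: residual variance (1−ρ)(1+2ρ)/(1+ρ), times 1+2/45 for estimating two covariates, F(1,46). At ρ = 0.4 the residual variance is 0.6×1.8/1.4 = 0.771 and the SE is √[(2/25)×0.771×1.044] = 0.254, giving 64%.

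| d | ρ | Main effect | Interaction | 1-df contrast | ANCOVA, two covariates |
|---|---|---|---|---|---|
| 0.4 | 0.4 / 0.6 / 0.8 | 9 / 8 / 8% | 24 / 34 / 62% | 31 / 43 / 72% | 34 / 45 / 71% |
| 0.6 | 0.4 / 0.6 / 0.8 | 15 / 13 / 12% | 49 / 67 / 94% | 59 / 77 / 97% | 64 / 78 / 97% |
| 0.8 | 0.4 / 0.6 / 0.8 | 22 / 19 / 17% | 75 / 91 / 99.7% | 83 / 95 / 99.9% | 87 / 95 / 99.9% |

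At d = 0.6, naming a 1-df contrast adds about 10, 9 and 3 points to the interaction's power. Covariate adjustment adds a further 5, 2 and 0.

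**Cramp logs, two periods**

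- Interaction, equivalent to a change-score test: variance 2(1−ρ), F(1,48).
- ANCOVA: variance 1−ρ², times 1+1/46, F(1,47).

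| d | ρ | Interaction | ANCOVA |
|---|---|---|---|
| 0.4 | 0.4 / 0.6 / 0.8 | 24 / 34 / 59% | 32 / 40 / 63% |
| 0.6 | 0.4 / 0.6 / 0.8 | 48 / 64 / 91% | 61 / 73 / 93% |
| 0.8 | 0.4 / 0.6 / 0.8 | 72 / 87 / 99% | 85 / 93 / 99.5% |

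The ratio of ANCOVA to change-score variance is (1+ρ)/2, apart from the penalty. The change-score test on 50 subjects is therefore as precise as ANCOVA on 50×(1+1/46)×(1+ρ)/2 subjects: 35.8, 40.9 and 46.0 at ρ = 0.4, 0.6 and 0.8.

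**Simulation.** With 20,000 trials per setting at d = 0.6, interaction / contrast / ANCOVA rejected in 49.0/59.0/64.2, 67.6/76.9/78.3 and 93.6/96.6/96.5% for the questionnaires. For the logs, interaction v ANCOVA gave 47.6 v 61.2, 64.4 v 73.2 and 90.8 v 92.9%. At d = 0 every test rejected in 4.7–5.4%.

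**Tukey family.** If the family is all six group-by-visit means, the critical value on 48 df is 2.97 instead of 2.01. Power for the unadjusted Post Treatment difference at d = 0.8 then falls from 79% to 45%.

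**Cost in df.** Error df go from 48 to 47 or 46, and critical t from 2.011 to 2.012 or 2.013. At ρ = 0 the SE of the Post Treatment difference rises from 0.283 unadjusted to 0.286 (one covariate) or 0.289 (two). Adjustment breaks even with that unadjusted comparison at ρ of about 0.15 or 0.16.

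**The case against.** The strongest reply is that nothing here is invalid. R-ANOVA with Tukey follow-up is a conventional analysis for this design, its interaction holds the 5% level, and the Tukey set can include the Post Treatment pair. That stands: the fault is inefficiency and an unnamed comparison, not bias. The low main-effect power also deserves little weight on its own, since the interaction is available.

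Second, for the questionnaires adjustment adds little once a focused contrast is named, and nothing at ρ = 0.8. There the SE of two-covariate ANCOVA is 1.003 times that of the contrast, and 1.013 times at ρ = 0.9. This also stands, but the plan names no such contrast. Its own test is the interaction, and the adjusted comparison had at least that test's power at every ρ tried from 0 to 0.9. At ρ = 0 and d = 0.6 it has 53% against 31%.

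Third, d, ρ and the equal-correlation structure are assumed, 25 per arm is a maximum, and the log figures need period summaries although the plan does not say how nights enter the model. Cramp frequency is a count, so its summary may not be normal. The size of the gain is therefore uncertain. The missing contrast does not depend on any of these assumptions.

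Finally, the section is in the past tense. If results have been seen, a new ANCOVA is post hoc and must be labelled so.

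**Conclusion.** The concern holds. The plan does not say which estimate shows whether Foam B beats Foam A after treatment, and it uses pre-randomisation scores as outcomes when they would serve better as covariates. Under the assumptions above, at d = 0.6 the adjusted contrast gains about 15, 11 and 3 points of power over the interaction for the questionnaires at ρ = 0.4, 0.6 and 0.8. The gains for the cramp logs are about 14, 9 and 2 points. Most of the questionnaire gain comes from naming a 1-df contrast; all of the log gain comes from adjustment. The type I error of the interaction is not in question. The change should be made, but the trial's validity does not turn on it. Confidence in the size of the gain is moderate, because the documents supply neither the correlation nor the effect.

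**What to change.** For each questionnaire, name the Foam B minus Foam A difference at Post Treatment as the single planned contrast. Estimate it by ANCOVA of the Post Treatment score on group, with the Baseline and Post Control scores as covariates. For cramp frequency and for severity, define one summary per 14-night period and regress the treatment-period value on group and the same subject's no-treatment-period value. The plan's phase 1 check of parametric assumptions should cover these summaries. Report each adjusted difference with a 95% CI. Label any R-ANOVA or Tukey output supportive, and state the comparison family and error term. If unblinded results have already been seen, label the ANCOVA post hoc.

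The cost is analysis wording, plus one df for the logs or two for the questionnaires. No further subjects, visits or measurements are needed.
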